### **7.10.11 Laboratory Studies**

#### **7.10.11.1 Complete blood counts**

A complete blood count including Hemoglobin, WBC, platelets, and differential will be obtained from each patient within 14 days of registration, at cycle 1 day 1, cycle 1 day 12, cycle 1 day 26, cycle 2 day 12, cycle 2 day 26, on day 26 of all subsequent cycles, and at the end of study treatment.

#### **7.10.11.2 Chemistry Studies**

Serum chemistries including BUN, creatinine, total bilirubin, ALT, AST, GGT, alkaline phosphatase, albumin, total protein, calcium, sodium, magnesium, potassium, phosphorous, glucose, LDH, amylase, and lipase will be assessed in each patient within 14 days of registration, at cycle 1 day 1, cycle 1 day 12, cycle 1 day 26, cycle 2 day 12, cycle 2 day 26, on day 26 of all subsequent cycles, and at the end of study treatment.

#### **7.10.11.3 Lipid Profile Studies**

Serum total cholesterol, triglycerides, LDL, and HDL will be assessed in each patient within 14 days of registration, at cycle 1 day 26, cycle 2 day 26, on day 26 of all subsequent cycles, and at the end of study treatment.

#### **7.10.11.4 Coagulation Studies**

PT/INR, PTT, and fibrinogen will be assessed in each patient within 14 days of registration, at cycle 2 day 26, and as clinically indicated for all subsequent cycles.

#### **7.10.11.5 Urine Studies**

Urine dipstick and urinalysis with specific gravity, pH, protein, blood, glucose, WBC, RBC, bacteria, and casts will be assessed in each patient within 14 days of registration. Urine dipstick must be negative for protein or, if documentation of +1 (+2 for patients with renal cell carcinoma) results for protein on dipstick reading, then total urinary protein  $\leq 500$  mg and measured creatinine clearance  $\geq 50$  mL/min/1.73m^2 must be attained from a 24 hour urine collection. Additional urine dipstick and microscopic studies will be performed only as clinically indicated in subsequent treatment cycles.

#### **7.10.11.6 Thyroid Function Studies**

TSH, T3, and T4 will be assessed in each patient within 14 days of registration, on cycle 3 day 26 ( $\pm 5$  days), cycle 6 day 26 ( $\pm 5$  days), and at the end of study treatment.

#### **7.10.11.7 Cardiac Enzyme Studies**

CPK, CK-MB, and troponin (T or I) will be assessed in each patient within 14 days of registration and only as clinically indicated in subsequent treatment cycles.

#### **7.10.11.8 Pregnancy Testing Studies**

A serum pregnancy test will be assessed in female patients of child-bearing potential within 14 days of registration and on day 26 ( $\pm$  5 days) of all subsequent treatment cycles.

### **7.10.12 Efficacy**

#### **7.10.12.1 6-month Complete Response Rate (6-month CR rate)**

The 6-month complete response (CR) rate is defined as the proportion of patients treated with dovitinib with no evidence of any remaining urothelial carcinoma tumors of any T-stage (including Tis) present within the bladder as assessed by standard of care cystoscopic examination with TURBT and urine cytology performed at 6 months after initiation of study therapy.

**NOTE:** Patients with residual non-invasive UC tumors with no component of carcinoma in situ (i.e. Ta, T1) at 3-month cystoscopy and TURBT are not considered relapses and will be permitted to continue on dovitinib therapy. If the subsequent 6-month cystoscopy, TURBT, and urine cytology shows no evidence of any remaining urothelial carcinoma in such patients, they will be considered a complete response. Patients with any component of carcinoma in situ (CIS) at 3-month cystoscopy/TURBT will be considered relapses and will not continue on dovitinib therapy. Any non-invasive UC tumors (i.e. Ta, T1, Tis) at the 6-month or any subsequent cystoscopy/TURBT is considered relapsed disease. Similarly progression to invasive UC tumors (T2-T4) at any time point is also considered relapsed disease and patients will not continue on dovitinib therapy.

#### **7.10.12.2 Relapse Free Survival (RFS)**

Relapse Free Survival (RFS) is defined as the time from study registration until the occurrence of any of the following relapse events:

1. Evidence of any component of CIS at 3-month cystoscopy/TURBT
2. Recurrent tumor  $\geq$  T2 at any time point
3. Recurrent tumor of any stage that occurs at or after the 6-month cystoscopy evaluation as assessed by bladder cystoscopy, TURBT, or urine cytology. Note: While not required as part of the study follow-up testing, positive urine FISH test (even if an isolated finding) at or after the 6-month study evaluations will be considered relapsed disease.
4. Documentation of metastatic urothelial carcinoma at any time point

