(22%) were the most commonly observed treatment related toxicities. Complete response was observed in 13 patients (41%) (Greenberg et al., 1997). In a larger phase II study of intravesical valrubicin according to the phase I dose and schedule but restricted to a patient population of 90 BCG-refractory carcinoma in-situ UC patients, Steinberg et al observed a complete response rate at six months of 21% (19 patients). Of the patients with complete response at six months, 13 maintained their response 12 months or greater duration for a 12-month recurrence free rate of 14%. Forty-four patients underwent cystectomy with 6 patients (7%) observed to have pathologic T3 or greater disease. A toxicity profile similar to the phase I valrubicin experience was observed with urinary frequency (66%), urinary urgency (63%), and dysuria (60%) as the most commonly reported side effects.(Steinberg et al., 2000) Based on these trial results, valrubicin was originally approved by the FDA for the treatment of BCG-refractory UC carcinoma in-situ patients in 1998 and later re-approved in May 2007 for the same indication after manufacturing quality concerns were addressed (2010b).

Collectively, gemcitabine and valrubicin both demonstrate promising initial complete response rates in BCG-refractory UC patients. However, both agents produce durable remissions of greater than 1 year in only 10-15% of patients. Therefore, a need clearly exists to explore the clinical efficacy of novel agents in this high-risk NMIBC population.

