#### **5.1 Inclusion Criteria**

Patients eligible for inclusion in this study have to **meet all** of the following criteria:

1. Histologically confirmed non-muscle invasive urothelial carcinoma of the bladder defined as Ta, T1, or Tis stage. Tumor staging must be confirmed by TURBT performed within 42 days prior to registration.
2. Presence of either an FGFR3 mutation or FGFR3 over-expression within bladder tumor tissue. Somatic FGFR3 mutations (see Table 1-2) in exons 7, 10, and 15 will be assessed in FFPE tumor tissues by massively parallel sequencing analysis utilizing the Ion Torrent Personal Genome Machine (PGM) and performed in the CLIA-certified Molecular Pathology and Translational Research Laboratory at the Dartmouth Hitchcock Medical Center. FGFR3 over-expression will be assessed by standard IHC analysis performed within the Indiana University Simon Cancer Center Immunohistochemistry (IHC) Core Lab.

NOTE: Patients will initially be allowed to enroll if their tumors demonstrate either an FGFR3 mutation or FGFR3 over-expression. However, a minimum of 10 FGFR3

mutation positive patients will be enrolled at study completion. If 10 patients with tumors that are FGFR3 over-expressors but FGFR3 mutation negative are accrued prior to enrolling 10 FGFR3 mutation positive patients, subsequent enrollment will be restricted to patients with tumors that are FGFR3 mutation positive.

3. Documented BCG-refractory disease defined as failure to achieve a tumor free state after at least 2 prior intravesical treatment courses, one of which must have been intravesical BCG therapy.

**NOTE:** There is no maximum limit on the number of prior BCG therapy courses. In addition, there is no maximum limit on the number of prior non-BCG intravesical therapy courses (i.e. gemcitabine, valrubicin, interferon, mitomycin C, etc.).

4. Medically unfit to undergo cystectomy or electively choosing to forego cystectomy

5. ECOG (WHO) performance status 0 or 1 or 2

6. Age  $\geq$  18 years old

7. Patients must have the following laboratory values:

- White blood cell count (WBC)  $\geq$  3.0 K/mm^3
- Absolute neutrophil count (ANC)  $\geq$  1.5 K/mm^3
- Platelets  $\geq$  100 K/mm^3
- Hemoglobin (Hgb)  $\geq$  9 g/dL
- Serum total bilirubin:  $\leq$  1.5 x ULN
- ALT and AST  $\leq$  3.0 x ULN

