### **7.10.12.3 1-year Relapse Free Survival (1-yr RFS)**

1-year RFS is defined as the proportion of patients who do not fulfill any of the relapse definitions in section 7.10.11.2 one year after study registration.

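### Relapse-free survival has no death event, so a patient who dies without documented relapse counts as a 1-year success or leaves the denominator, and either way the rate is biased upward

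*Combined protocol and SAP*

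**What the plan says.** Section 7.10.12.2 opens with "Relapse Free Survival (RFS) is defined as the time from study registration until the occurrence of any of the following relapse events" and then lists four events:

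1. "Evidence of any component of CIS at 3-month cystoscopy/TURBT"
2. Muscle-invasive tumor (T2 or higher), whenever it is found
3. Later tumor, described as "Recurrent tumor of any stage that occurs at or after the 6-month cystoscopy evaluation as assessed by bladder cystoscopy, TURBT, or urine cytology" (a note adds a positive urine FISH test)
4. "Documentation of metastatic urothelial carcinoma at any time point"

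Section 7.10.12.3 turns this into a rate: "1-year RFS is defined as the proportion of patients who do not fulfill any of the relapse definitions" one year after registration. It refers the reader to 7.10.11.2, which is Chemistry Studies; the definitions are in 7.10.12.2. Section 3.2.1 words the same rate as the share of treated patients with no evidence of remaining tumor at 12 months of follow-up.

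For missing data, 10.1 treats the two kinds of endpoint differently. A patient who starts therapy but does not reach the primary evaluation counts as not having a CR, and the plan calls this conservative. Secondary outcomes are not imputed and are analyzed on complete cases. Section 10.6.2 reports the 1-year rate with a 90% Agresti-Coull interval, and 10.7.1 uses Cox regression for RFS without a censoring or competing-event rule.

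**The concern.** An endpoint called a survival endpoint normally fails a patient who dies. Here the list is fixed and death is not on it, so the literal rule scores a death without documented relapse as a success. Such deaths are foreseeable: patients enter as "Medically unfit to undergo cystectomy or electively choosing to forego cystectomy", ECOG 2 is allowed, and a Charlson index is collected at baseline.

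Cystectomy raises a related but smaller question. Residual Ta or T1 without CIS at 3 months is by rule not a relapse. If the bladder is removed at month 4 and the specimen shows pT1, none of the four events is met. Event 3 starts at the 6-month evaluation and names cystoscopy, TURBT and cytology, not a cystectomy specimen. Section 3.2.1 does use cystectomy histology, but only for progression to T2-T4.

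At stake is how the 1-year rate will be read. With 20 patients and background rates of 10-15%, one or two patients classified the wrong way change the impression the result gives.

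**Working it through.** **Is the gap closed elsewhere?** Take a patient who dies at month 5 with no documented relapse.

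- 7.10.12.2: no event is met.
- 7.10.12.3: no relapse definition is fulfilled, so the patient is relapse-free at 1 year.
- 3.2.1: no tumor has been seen, but there is no 12-month assessment, so the patient could be called a success or missing. Being alive is not required.
- 10.1: if missing, the patient leaves the denominator.
- 4.2 (end of study), 7.9 (follow-up) and 10.7.1 (Cox regression): no rule for death.

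No section makes this patient a failure.

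**Inputs.** n = 20 (10.8). Section 1.1.4 cites 12-month rates of 10% for gemcitabine and 14% for valrubicin. On 20 patients these are 20 × 0.10 = 2 and 20 × 0.14 = 2.8, so 2 to 3 successes. The plan states no expected value or power for 1-year RFS, so there is no figure of its own to reproduce. It also gives no rate of death without relapse; the number of such patients, d, is an assumption and is varied from 1 to 2.

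**Formulas.** Let x be the patients alive and without a relapse at 1 year.

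- Death as an event: x/20
- As written: (x + d)/20, which is 5 points higher per patient (1/20)
- Complete-case: x/(20 − d), which multiplies the rate by 20/(20 − d), or 1.05 for d = 1 and 1.11 for d = 2

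| x | d | Death as event | As written | Complete-case |
|---|---|---|---|---|
| 2 | 1 | 10.0% | 15.0% | 10.5% |
| 2 | 2 | 10.0% | 20.0% | 11.1% |
| 3 | 1 | 15.0% | 20.0% | 15.8% |
| 3 | 2 | 15.0% | 25.0% | 16.7% |
| 5 | 2 | 25.0% | 35.0% | 27.8% |

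Both routes move the rate up; complete-case leaves it unchanged only when x = 0.

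**Intervals.** Reading the 90% Agresti-Coull interval as two-sided (z = 1.645), use n' = n + z², p' = (x + z²/2)/n', and p' ± z√(p'(1 − p')/n'). For x = 2 and d = 2:

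- death as event, 2/20: 2.5% to 27.0%
- as written, 4/20: 8.9% to 38.2%
- complete-case, 2/18: 2.9% to 29.5%

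**Which cystectomies are missed?** CIS at 3 months, T2 or higher, metastasis, and any tumor seen by cystoscopy, TURBT or cytology from the 6-month evaluation on are already events, usually recorded before surgery. Two cases remain: cystectomy before the 6-month evaluation for residual Ta/T1 without CIS, and tumor below T2 found only in the specimen. Each such patient counts in d in the same way.

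**The case against.** **Missing is a fair reading.** Section 3.2.1 asks about status at 12 months of follow-up, which a patient who died at month 5 does not have. The effect is then 10% to 11.1% in the example, not 10% to 20%. This stands: the larger figure follows only from 7.10.12.3 read literally, and both sizes have to be shown. It does not remove the point, because dropping deaths still biases the rate upward.

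**Some early deaths may never enter the analysis.** Section 7.8 replaces patients withdrawn before the first post-therapy evaluation, and the efficacy set in 10.2.5 requires one such evaluation. No analysis set is named for RFS. This may reduce the number counted as successes, but it also removes failures.

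**Cystectomy looks like a large gap.** A reader might infer this from the cited valrubicin study of 90 patients, where "Forty-four patients underwent cystectomy". The documents do not support that inference. The study enrolled only CIS patients, and section 1.1.4 gives neither the timing of surgery nor whether relapse came first. In this trial CIS at 3 months is already an event. The figure says nothing about how often the two uncovered cases would occur.

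**RFS is not tested against 10-15%.** This is correct. That range is background, and 10.6.2 calls all secondary objectives hypothesis generating. The comparison is one a reader will make, not one the plan sets.

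**Conclusion.** The point holds for death. Sections 7.10.12.2 and 7.10.12.3 together state a rule that scores a death without documented relapse as 1-year relapse-free, and nothing else in the protocol corrects it. Each such patient among 20 adds 5 points as written, or multiplies the rate by 20/(20 − d) if dropped as missing. The direction is certain whenever there is at least one such patient and at least one true success. The size is not known, because the documents give no rate of death without relapse.

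For cystectomy the point holds only as a small residual gap.

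A reader might go further and conclude that the 1-year rate will be doubled, or that the endpoint was meant to show a retained, tumor-free bladder. Neither is supported. Doubling needs as many uncaptured patients as true successes plus the literal reading, and no section makes an intact bladder part of the endpoint. The 6-month CR analysis, which counts unevaluated patients as failures, is unaffected. This should be corrected, but it does not threaten the primary conclusion.

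**What to change.** - In 7.10.12.2 add death from any cause as an RFS event.
- In the same list, count as an event, dated at surgery, residual urothelial carcinoma of any stage in a cystectomy specimen, or cystectomy performed for persistent or recurrent disease.
- Align 3.2.1 and 7.10.12.3 with this list, and change the reference in 7.10.12.3 from 7.10.11.2 to 7.10.12.2. Do not add a separate bladder-in-place condition: it would fail a tumor-free cystectomy done for another reason and so contradict the event list.
- If a tumor-only measure is wanted, report it separately as a relapse rate with death as a competing event.

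The cost is mainly wording, and the reported rate will be slightly lower. Data capture needs a check. Section 7.9 limits safety follow-up to 30 days or 5 half-lives, 8.2.2.2 requires reporting of later deaths only if felt to be treatment related, and no section asks for a cystectomy date. Relapse follow-up under 7.9 may bring both to light, but the eCRF must be confirmed to record dates of death and cystectomy through 12 months.

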### 3.2.1 Endpoint for Secondary Objectives

- The 1-year relapse free survival rate is defined as the proportion of patients treated with dovitinib with no evidence of any remaining urothelial carcinoma tumors at 12 months of follow-up.

**NOTE:** Patients with residual non-invasive UC tumors with no component of carcinoma in situ (i.e. Ta, T1) at 3-month cystoscopy and TURBT are not considered relapses and will be permitted to continue on dovitinib therapy. If the subsequent 6-month cystoscopy/TURBT, and urine cytology shows no evidence of any remaining urothelial carcinoma in such patients, they will be considered a complete response. Patients with any component of carcinoma in-situ (CIS) at 3-month cystoscopy/TURBT will be considered relapses and will not continue on dovitinib therapy. Any non-invasive UC tumors (i.e. Ta, T1, Tis) at the 6-month or any subsequent cystoscopy/TURBT is considered relapsed disease. Similarly progression to invasive UC tumors (T2-T4) at any time point is also considered relapsed disease and patients will not continue on dovitinib therapy.

- The rate of progression to muscle-invasive stage for dovitinib is defined as the proportion of patients with clinical or pathologic progression to muscle-invasive stages (i.e. T2-T4) at any time point on study. Pathologic progression is assessed by histological finding at TURBT or cystectomy. Clinical progression is assessed by clinician's physical exam and findings on radiologic imaging as ordered per the treating physician's discretion.
- The 3- and 6-month partial response rates are defined as the proportion of patients treated with persistent but reduced T-stage tumors on post-therapy TURBT (i.e. T1 -> Ta; T1+Tis -> T1).
- Treatment related toxicity rates will be assessed by CTCAE v4.0.

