#### **7.10.7.3 Urine Fluorescent In-Situ Hybridization**

Testing of urine by fluorescent in-situ hybridization (FISH) for recurrence is not required at any time point as part of this study. The treating urologist may order commercial urine FISH testing (i.e. Urovysion®) at their own discretion.

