### **7.10.12.4 Complete Response (CR)**

Complete response (CR) is defined as disappearance of all bladder tumors (of any T-stage), both grossly and microscopically on urine cytology and post-treatment bladder biopsy.

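### An isolated positive urine FISH is an RFS event although FISH is unscheduled and discretionary, so 1-year RFS depends partly on test ordering and one patient can be a 6-month CR and relapsed at the same visit

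*Combined protocol and SAP*

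**What the plan says.** Section 7.10.12.2 lists the RFS events: any CIS at the 3-month cystoscopy/TURBT, tumor of stage T2 or above at any time, recurrence of any stage at or after the 6-month cystoscopy, and documented metastasis. A note to the third event adds that a "positive urine FISH test (even if an isolated finding) at or after the 6-month study evaluations will be considered relapsed disease".

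Section 7.10.7.3 says: "Testing of urine by fluorescent in-situ hybridization (FISH) for recurrence is not required at any time point as part of this study". It continues: "The treating urologist may order commercial urine FISH testing", at their own discretion. FISH does not appear in the visit schedule (Table 7-1).

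Section 7.10.12.3 defines 1-year RFS as the "proportion of patients who do not fulfill any of the relapse definitions in section 7.10.11.2 one year after study registration". In this protocol 7.10.11.2 is Chemistry Studies; the relapse list is 7.10.12.2. The cystoscopy and TURBT footnotes to Table 7-1 carry the same wrong number. Section 3.2.1 describes 1-year RFS more briefly, as patients "with no evidence of any remaining urothelial carcinoma tumors at 12 months of follow-up".

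Six-month CR (7.10.12.1) is judged "as assessed by standard of care cystoscopic examination with TURBT and urine cytology performed at 6 months after initiation of study therapy". The general CR definition (7.10.12.4) is "disappearance of all bladder tumors (of any T-stage), both grossly and microscopically on urine cytology and post-treatment bladder biopsy". The relapse NOTE, repeated in 3.1.1, 3.2.1, 7.10.7.1 and 7.10.12.1, does not mention FISH.

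**The concern.** An endpoint event should be one that every patient has the same planned opportunity to show. Here one event can occur only in patients whose urologist ordered an extra test. Two sites with identical patients but different ordering habits would report different 1-year RFS.

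The rule also begins at the 6-month evaluation itself, the visit at which the primary endpoint is read. Because CR ignores FISH and relapse does not, the two can be recorded for the same patient on the same date.

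Three things inherit the problem: the key secondary 1-year RFS rate, the univariate Cox regressions on RFS in 10.7.1, and duration of CR as defined in 7.10.12.10.

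**Working it through.** **No plan figure to reproduce.** The documents give no assumed rate or power for 1-year RFS, and no FISH ordering or positivity rate.

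**Step 1: classify one patient.** Take a patient at month 6 with clear cystoscopy, negative TURBT biopsies, negative cytology and a positive FISH.

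| Rule | Status |
|---|---|
| 7.10.12.1 and 7.10.12.4 (CR) | Complete response |
| Relapse NOTE (3.1.1, 3.2.1, 7.10.7.1, 7.10.12.1) | No listed relapse event |
| 7.10.12.2 (RFS events) | Relapsed |
| 7.10.12.10 (duration of CR) | Zero, if both carry the same date |

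The same patient without the FISH order is a complete responder and relapse-free. No section says which status prevails.

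**Step 2: effect of one patient.** Inputs: n = 20 (10.8), all assumed to contribute to RFS; 90% Agresti-Coull intervals (10.6.2), taken as two-sided, z = 1.645. With x relapse-free patients, p̃ = (x + z²/2)/(n + z²), and the limits are p̃ ± z·√[p̃(1 − p̃)/(n + z²)]. Here z² = 2.706 and n + z² = 22.706.

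- x = 3: p̃ = 4.353/22.706 = 0.192. Estimate 15%, interval 5.6% to 32.8%.
- x = 2: p̃ = 3.353/22.706 = 0.148. Estimate 10%, interval 2.5% to 27.0%.

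Each isolated positive in an otherwise relapse-free patient costs 1/20 = 5 points.

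**Step 3: illustrative range (assumed inputs only).** Let s be the share of otherwise relapse-free patients in whom FISH is ordered, and q the probability that a tested patient has at least one isolated positive. Reported RFS = base RFS × (1 − s·q), where base RFS is the rate without isolated FISH. From an assumed base of 15%:

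- q = 0.20: s = 0.25 gives 14.25%, s = 0.5 gives 13.5%, s = 1 gives 12.0%.
- s = 1: q = 0.10 gives 13.5%, q = 0.30 gives 10.5%.
- Extreme case, s = 1 with three independent tests (months 6, 9 and 12) each positive with probability 0.20: q = 1 − 0.8³ = 0.488, giving 7.7%. Positive correlation between tests in one patient would lower q and shrink this effect.

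**Step 4: can a FISH-free RFS be recovered at analysis?** Section 7.9 follows patients for relapse until relapse is noted, and 10.1 uses complete cases for secondary outcomes. Suppose three patients are relapse-free on the other events, one has an isolated positive FISH, and relapse follow-up stops there. That patient's 12-month status without FISH is then missing, and the complete-case result is 2/19 = 10.5%, not 3/20 = 15%. The later assessments must be collected if the FISH-free rate is to be computed.

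**The case against.** The strongest reply is that the rule is openly stated, can only lower RFS relative to not counting FISH, and so is a deliberate conservative choice on an endpoint that 10.6.2 calls hypothesis generating. There is one arm, so no between-arm bias. All of that stands and limits the weight of the point. It does not make the event equally ascertained across patients.

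A reader might infer that the reported rate would be set by site habit rather than disease, or that every isolated positive is false. The documents do not support that: they say nothing about FISH accuracy, and some isolated positives may be true early recurrences. The base rate in the working is therefore a rate under a different definition, not a true rate.

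A reader might also infer that FISH rules out comparison with the 10% and 14% 12-month rates in 1.1.4. No such RFS comparison is planned, 1.1.4 itself warns that between-study comparison is difficult, and the 14% comes from a CIS-only cohort.

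The silence of 3.2.1 is not by itself a contradiction, since its 1-year RFS sentence names no test. The relapse NOTE is better evidence, though it also omits metastasis and so is not a full event list. Nor is overlap between CR and relapse unique to FISH: CR concerns the bladder, and a patient with a clear bladder and metastasis would also be both. What is missing is a stated precedence.

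Finally, simply striking FISH from the relapse events could change when treatment (7.6) and relapse follow-up (7.9) end. That objection is sound, and the fix is confined to the analysis definition.

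**Conclusion.** The point holds for 1-year RFS and the analyses built on relapse. Under 7.10.12.2, the same patient gets a different RFS outcome depending on whether an optional test was ordered, and can be a CR and relapsed at the same visit with no rule to resolve it.

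The size cannot be estimated from the documents. What follows from the design is the step of 5 points per isolated positive if all 20 patients contribute. Section 1.1.4 puts durable remission at 10-15%, so one such patient can move the estimate from one end of that range to the other, although the 90% intervals before and after overlap heavily. The percentages in Step 3 rest wholly on assumed rates.

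A reader might infer that the primary endpoint is compromised. It is not: 6-month CR does not use FISH, and its definition and the sample size are untouched. This is a modest, inexpensive correction to a secondary endpoint.

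**What to change.** For analysis only:

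1. Define the main RFS analysis by the events in 7.10.12.2 without isolated FISH: CIS at 3 months; T2 or greater at any time; recurrence at or after month 6 on cystoscopy, any TURBT/biopsy (including clinically triggered ones) or cytology; and documented metastasis. The CR definition stays as it is, so the conflict disappears from the main analysis.
2. Record FISH ordering, dates and results in the eCRF.
3. Keep collecting the planned tumor assessments after an isolated positive FISH, so that RFS can be computed both ways.
4. Report RFS counting isolated FISH as events as a sensitivity analysis.
5. Correct the cross-reference in 7.10.12.3 to 7.10.12.2, and likewise in the footnotes to Table 7-1.

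Separately, 7.6, 7.9, 7.10.12.2 and the relapse NOTE must be reconciled on whether an isolated positive FISH is relapse for treatment and follow-up. No clinical rule is proposed here.

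The cost is a short definition, a few eCRF fields, continued assessment data for any affected patients, and one table. The downside is that some true early recurrences would be dated later in the main analysis. Some discretion remains in any case, because TURBT after month 6 and imaging after baseline are left to the treating physician.
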